6.4.3. Adverse Events

According on the onset date of the event, AEs will be defined as follows:

- Treatment-emergent AEs (TEAEs), those events with an onset date after study treatment initiation.
- Non-treatment-emergent AEs (non-TEAEs), those events with an onset date between informed consent and study treatment initiation.

An overview of TEAEs will be provided for the number of patients with any TEAEs, numbers of TEAEs, number of patients with serious TEAEs, number of serious TEAEs, number of patients with TEAEs leading to interruption of study treatment, number of patients with TEAEs leading to withdrawal of study treatment, number of patients with fatal TEAEs, number of patients with mild/moderate/severe TEAEs, number of patients with TEAEs related/not related to study treatment.

AEs for which relationship to study drug is not specified or unknown will be considered treatment related.

The incidence of TEAEs will be tabulated by System Organ Class (SOC) and Preferred Term (PT), and by SOC and PT and severity by treatment group. A subject with multiple occurrences of an AE will be counted only once in the AE category. These analysis will be repeated for all the above categories.

Sponsor: ITALFARMACO
Protocol: DSC/15/2357/53

TEAE will be summarized under the worst severity recorded for the event.

Deaths, SAEs and AEs leading to withdrawal of study treatment will also be listed.

Non-treatment emergent AEs will only be listed.

6.4.4. Laboratory parameters

The absolute value and change from baseline will be analyzed for each laboratory parameters separately for hematology, biochemistry, coagulation, serology and urinalysis by means of summary descriptive statistics at each time point, by treatment group. In addition, shift tables using the low/normal/high classification to compare baseline to the worst ontreatment value will be provided.

Listings of all laboratory data with values out of range will also be provided.

In addition, the following summaries in relation to post-baseline platelet counts will be presented by treatment group: minimum values, time to nadir (days) and time to recovery (days). These will be defined as follows:

Minimum value = minimum post-baseline platelet count for the subject.

Time to nadir (days) = time from the date of first drug administration to first minimum post-baseline value regardless if this is within the normal range.

Time to recovery (days) = for subjects whose minimum post-baseline value is below the lower limit of normal, the time to recovery is calculated as the time from the minimum value below lower limit of normal to the first value within the normal range.

Furthermore, the above summaries will be repeated for patients who reduced dose at least once due to platelet count decrease. Moreover, for this subgroup of patients, the following variables will be described as well:

- time on treatment after recovery (days), additional platelet decrease after recovery, time on treatment without recovery (days), where:
- time on treatment after recovery = for subjects who record recovery from the minimum value below the lower limit of normal, the time on treatment after recovery is calculated as the time from the date of recovery to the last treatment date or date of data cut-off.
- additional platelet decrease after recovery = number of subjects who record recovery from the minimum value below the lower limit of normal and then record a subsequent value below the lower limit of normal.
- time on treatment without recovery = for subjects who do not record recovery from
 the minimum value below the lower limit of normal, the time on treatment without
 recovery is calculated from the date of the minimum value below the lower limit of
 normal to the last treatment date.

Sponsor: ITALFARMACO
Protocol: DSC/15/2357/53

A box-plot will be produced for the following parameters over time by treatment group: platelets, hemoglobin, neutrophils, leukocytes, triglycerides and total cholesterol.

Pharmacokinetics

Finally, pharmacokinetic parameters (ITF2374 and ITF2375) for patients treated with givinostat will be listed by patient together with the IMP dosage. Further details will be provided in a separate SAP.

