4.4.2. Handling of Missing Data/Imputation/Censoring Rules

For the primary efficacy endpoint, defined as mean fibrosis % from baseline to 12 months of therapy, as well as for the key secondary endpoint (MRI) different multiple imputation approaches will be applied to handling missing data. Further details on the missing imputation strategies are provided in Section 6.3.1 of the present document for the primary efficacy endpoints, and in Section 6.3.2.2 and 6.3.2.3 for the key secondary endpoints.

Results for the other efficacy and safety endpoints will be based on non-missing data only (i.e. missing observations will not be replaced).

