6.4. Safety Evaluation

Safety analysis will be performed on the Safety Set and will be reported by actual treatment group. No methodology for missing data handling will be applied for safety parameters.

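### Time to platelet recovery has no censoring rule, so patients who never return to normal drop out of that by-arm summary

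*SAP*

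**What the plan says.** SAP section 6.4.4 plans three platelet summaries by treatment group: minimum post-baseline value, time to nadir and time to recovery. For patients whose minimum is below the lower limit of normal (LLN), "the time to recovery is calculated as the time from the minimum value below lower limit of normal to the first value" in the normal range. The section does not say what happens to a patient with no later normal count, names no estimator, and does not ask for the number not recovered.

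The general rules do not fill the gap. Section 4.4.2, whose title includes censoring rules, says "Results for the other efficacy and safety endpoints will be based on non-missing data only" and gives no censoring rule. Section 6.4 says "No methodology for missing data handling will be applied for safety parameters". Section 4.1 sets the default for continuous data: mean, SD, median, quartiles and range.

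Section 6.4.4 does foresee non-recovery. It says "the above summaries will be repeated for patients who reduced dose at least once due to platelet count decrease", and then that "for this subgroup of patients, the following variables will be described as well". One of these is the duration variable that begins "time on treatment without recovery = for subjects who do not record recovery from" a minimum below LLN; it runs from that minimum to the last treatment date. It is defined for this subgroup only and is not combined with the recovery times.

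**The concern.** Time to recovery is a time-to-event quantity, and some patients may leave observation before the event. With no censoring rule, the default summary is computed on those who had the event. Non-recovered patients do not lengthen the summary; they disappear from it, and nothing beside it says how many there were.

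Platelets matter in this trial. Protocol Amendment 2 reports that 11 of the first 21 patients needed a dose reduction for thrombocytopenia. On the sponsor's assumption that 14 of the 21 were on givinostat, that is 11/14 = 79%, and the starting dose was changed. How long counts stay low is therefore something a reader of the study report will look for, and a median based on recovered patients alone could be taken as describing everyone who fell below LLN.

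**Working it through.** **Plan's own figure.** There is none to reproduce. The documents give no expected recovery time on treatment and no non-recovery rate. Protocol section 4.2.2 says that in earlier studies platelet reductions resolved within 2 to 3 weeks of stopping treatment. It also says that counts reached a nadir after 2 to 3 weeks of treatment and then a plateau.

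**Step 1: direction, with no distributional assumption.** At a recovery time with *d* recoveries, let *R* be the recovered patients whose recovery is at or after that time, and *N* the non-recovered patients still under observation.
- Recovered-only summary: hazard = *d*/*R*.
- Kaplan-Meier: hazard = *d*/(*R* + *N*), which is never larger.

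The Kaplan-Meier curve for remaining unrecovered therefore lies on or above the recovered-only curve at every time, so the recovered-only median cannot exceed the Kaplan-Meier median. The curves coincide only if *N* = 0 at every recovery time.

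**Step 2: size when follow-up ends before recovery.** Assumptions, not from the documents: recovery is exponential with true median *m*, so λ = ln 2/*m*; follow-up after the nadir is uniform on 30 to 336 days.
- Share with no recorded recovery: *p* = (e^(−30λ) − e^(−336λ))/(306λ).
- Recovered-only median *t* solves P(T ≤ *t*, T ≤ C) = 0.5(1 − *p*), where T is recovery time and C is follow-up. For *t* ≤ 30 this gives *t* = −ln((1 + *p*)/2)/λ; above 30 it is solved numerically.

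Example, *m* = 21: λ = 0.03301; *p* = 0.037; *t* = −ln(0.5184)/0.03301 = 19.9 days.

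| True median (days) | Not recovered | Median shown (days) |
|---|---|---|
| 14 | 1.5% | 13.7 |
| 17.5 | 2.5% | 16.9 |
| 21 | 3.7% | 19.9 |
| 42 | 12.0% | 35.2 |
| 84 | 28.4% | 54.7 |

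**Step 3: size when a share π never recovers.** Assumptions: recovered patients have an exponential distribution with median 17.5 days (midpoint of 2 to 3 weeks), and non-recovered patients stay under observation. The all-patient median is −ln(1 − 0.5/(1 − π))/λ, with λ = ln 2/17.5 = 0.0396. The recovered-only summary shows 17.5 days throughout. The all-patient median is 20.5 days at π = 10%, 24.8 at 20%, 31.6 at 30% and 45.2 at 40%; at 50% it is not reached.

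**Step 4: who is left out altogether.** A patient below LLN who does not recover and had no platelet-related dose reduction has neither a recovery time nor the subgroup's duration variable. A patient stopped permanently without a prior reduction is one example. Protocol section 7.3.1 has such patients followed until the event resolves or stabilises, and a stable count need not be a normal one.

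**The case against.** The case that this matters little is a good one, and much of it stands.

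- **Off-treatment counts will capture many late recoveries.** Completers have hematology at the Week 52 visit, four weeks after the last dose, and section 6.4.4 does not limit recovery to on-treatment values. Given the earlier resolution after stopping, a completer who was low throughout would often record recovery there and enter the summary with a long time. A reader might infer that the slow cases are the ones removed; the documents do not support that, because slow recoverers who eventually normalise are kept. The visit is planned for completers only, however, and the 2-to-3-week figure concerns recovery after stopping, not on continued treatment.
- **The dose-reduced subgroup may hold most persistent cases.** Protocol section 7.3.1 ties dose reduction to two consecutive counts at or below 150 x 10^9/L. If LLN is about that level or lower (the documents do not state it), most patients persistently below LLN on treatment would fall in the subgroup. This narrows the group with no variable at all, but does not put non-recovered patients into the recovery-time summary.
- **Other outputs do not depend on recovery.** The SAP also says "shift tables using the low/normal/high classification to compare baseline to the worst ontreatment value will be provided", and plans minimum values, time to nadir, out-of-range listings and platelet box-plots. A reader might infer that platelet safety reporting as a whole is biased; it is not. Comparing the number whose worst value is low with the number who have a recovery time gives a rough count of non-recovery, but the reader must assemble it.
- **Sparse sampling works the other way.** After Week 12, scheduled hematology is 12 weeks apart until Week 48, so the first normal count may be recorded late. A reader might infer that reported recovery must be faster than true recovery; the net error against true recovery time cannot be signed. This is a separate error and does not cancel the exclusion.

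**Conclusion.** The point holds for one descriptive output. As written, the by-arm time-to-recovery summary leaves out patients with a nadir below LLN who never record a normal count. It can match a censored analysis of the same data or show faster recovery, but never slower. That direction needs no distributional assumption.

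The size is unknown because the documents give no non-recovery rate. Under the exponential and 30-to-336-day assumptions, it is negligible if true medians are 14 to 21 days (about 2% to 4% excluded) and material at 42 to 84 days (12% to 28% excluded). If everyone recovers, there is no effect. No test, sample size or primary result depends on this output. The change is worth making because the SAP itself expects some patients not to recover and the repair uses data already collected.

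**What to change.** In SAP section 6.4.4, for all patients with a nadir below LLN:
1. Report by arm the number with such a nadir and the number with no later normal count.
2. Summarise time to recovery by Kaplan-Meier, censoring non-recovered patients at their last platelet count.
3. Repeat both in the subgroup that reduced dose because of platelets.
4. Extend the non-recovery duration variable from that subgroup to all such patients.

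The cost is SAP wording and standard code, with no new data. The drawback is small numbers: 34 givinostat and 17 placebo patients are planned and only those below LLN contribute, so some medians will be imprecise or not reached. The counts in item 1 remain informative even then.

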as 50 mg o.d. or 50 mg b.i.d. the decreases in platelet counts were well confined within the range of normality. The majority of reductions in platelets were mild and occurred usually within the first week after treatment initiation and reached a nadir point after 2 to 3 weeks of treatment and then a 'plateau." All occurrences resolved fully within 2 to 3 weeks following discontinuation of therapy, suggesting a rapidly reversible effect. The majority of thrombocytopenic events were mild in severity with fewer than 10% of subjects developing platelets count below 75 x 10^9/L. In order to prevent any severe thrombocytopenia, close monitoring of hematology values will be implemented during the study.

Overall, sixteen hemorrhagic drug-related AEs were reported by 14 patients in the completed clinical trials with givinostat. However, only in seven of these cases were the hemorrhagic drug-related AEs in patients with concomitant thrombocytopenia; these were all oncology patients and, in some thrombocytopenia, up to grade 4 was already present before givinostat treatment started. In all the remaining cases (nine hemorrhagic drug-related AEs occurring in seven subjects), platelet counts at the time of the hemorrhagic AE were either within normal range or above the upper limit of normal. None of the drug-related hemorrhagic episodes were observed in DMD subjects.

Most premature discontinuations seen in completed or discontinued studies were associated with a decrease in platelet counts. Discontinuations due to this reason were mainly confined to the 100 mg b.i.d. dose. Other causes of premature discontinuations were mostly related to worsening of disease under study.

Cases of mild upper respiratory tract infections were reported in subjects treated with ITF2357. Five patients with multiple myeloma experienced severe systemic infections.

Overall, treatment with ITF2357 of both healthy volunteers and patients did not show clinically meaningful changes for any of the measured chemistry parameters, with the exception of a transient and slight increase in serum creatinine levels observed in only one study in Crohn's disease patients.

There was no evidence of general systemic toxicity reflected by changes in vital signs in the studied populations. Finally, although some episodes of QTc prolongation were reported (90% of those reported in oncological studies), no events of clinical concern or dose related trend were seen.

17 June 2020 Page 36 of 110

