## 9.1.11 Follow-up Visit (Week 52) (± 7 days)

The follow-up visit will be performed 4 weeks after the last dose is administered ( $\pm 7$  days).

The following assessments will be performed:

- Concomitant medications
- Physical examination
- Vital signs (blood pressure, heart rate and body temperature)
- 12-lead ECG
- Blood collection for
  - hematology
  - blood chemistry
  - coagulation tests (PT and aPTT)
  - thyroid function tests (TSH, fT3, fT4)
- Urine analysis
- AE assessments

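### SAP 6.4.4 counts normal platelet values taken off drug as recovery, so washout after the last dose can enter the 'on treatment' recovery variables, with a negative duration

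*SAP*

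**What the plan says.** SAP 6.4.4 builds its platelet summaries on two definitions. The nadir is taken over everything after baseline: "Minimum value = minimum post-baseline platelet count for the subject". For patients whose minimum is below the lower limit of normal (LLN), time to recovery is the "time from the minimum value below lower limit of normal to the first value within the normal range". Neither definition says whether the patient must be on study drug when the count is taken. The shift tables in the same section are limited to treatment (the wording is "compare baseline to the worst ontreatment value will be provided").

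These summaries are then "repeated for patients who reduced dose at least once due to platelet count decrease", and three variables are added for that subgroup:

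- *Time on treatment after recovery*, which "is calculated as the time from the date of recovery to the last treatment date or date of data cut-off".
- *Additional platelet decrease after recovery*, the number of patients who recover and later record another value below LLN.
- *Time on treatment without recovery*, defined "for subjects who do not record recovery from" the sub-normal minimum, and running from the date of that minimum to the last treatment date.

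The protocol provides for off-drug platelet counts in three situations:

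- **Visit 12.** Section 9.1.11 states: "The follow-up visit will be performed 4 weeks after the last dose is administered", with a window of ±7 days. Haematology is on its list, and Table 5 (footnote 6) includes platelets in that panel.
- **Early withdrawal.** Section 9.1.10 includes haematology at a visit within four weeks of the last dose.
- **Temporary interruption.** For a count below 75 but above 50 x 10^9/L, Section 7.3.1 stops treatment and repeats the count until it is normal.

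On platelet reductions in earlier studies, Section 4.2.2 says: "All occurrences resolved fully within 2 to 3 weeks following discontinuation of therapy".

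**The concern.** The three subgroup variables are there to describe what happens to platelets while a patient stays on treatment after a platelet-driven dose reduction. That calls for separating a count that normalises on the reduced dose from one that normalises because the drug has been stopped. The written definition does not separate them: any normal value after the nadir qualifies.

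Two results follow for a patient who first normalises after the last dose. He is moved from the non-recovery variable to the recovery variable, and his duration on treatment after recovery runs backwards in time. The misclassification goes one way: a patient who did not recover on drug is shown as recovered. The question matters clinically, because Amendment 2 changed the starting dose after 11 of the first 21 patients needed a reduction for thrombocytopenia.

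**Working it through.** The plan gives no figure for this point, so the check is day arithmetic on its own schedule.

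**Inputs**

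- Last dose: week 48, day 48 x 7 = 336 (Protocol 9.1.10, nominal).
- Visit 12: last dose + 28 days, ±7, so 21 to 35 days after the last dose (Protocol 9.1.11).
- Early Withdrawal Visit: 0 to 28 days after the last dose (Protocol 9.1.10).
- Platelet washout in earlier studies: 2 to 3 weeks, so 14 to 21 days (Protocol 4.2.2).

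**Step 1: sign of the duration.** Time on treatment after recovery = last treatment date - recovery date. If the first normal count after the nadir is at Visit 12:

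- nominal: 336 - (336 + 28) = -28 days
- early edge of window: 336 - (336 + 21) = -21 days
- late edge of window: 336 - (336 + 35) = -35 days

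**Step 2: the other end date.** With data cut-off instead, the value is cut-off - Visit 12 date. It can be zero or positive, but every day in it falls after the last dose. The SAP does not say which date applies.

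**Step 3: worked patient.** Nadir below LLN at week 36 (day 252), still low at the last dose (day 336), normal at Visit 12 (day 364).

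| | As written | Recovery limited to on-drug counts |
|---|---|---|
| Time to recovery | 364 - 252 = 112 days | no on-drug recovery |
| Time on treatment after recovery | 336 - 364 = -28 days | not applicable |
| Time on treatment without recovery | patient excluded | 336 - 252 = 84 days |

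With the nadir at week 24 (day 168), time to recovery as written is 364 - 168 = 196 days. The restricted rule gives 336 - 168 = 168 days without recovery.

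**Step 4: would the Visit 12 count be normal?** Visit 12 falls 21 to 35 days after the last dose, at or beyond the 14 to 21 days reported for washout. If that experience carries over, a completer still low at the last dose would be expected to be normal by Visit 12. An early withdrawal seen before day 14 might still be low; one seen from day 21 would be expected to be normal.

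**Step 5: interruptions.** Section 7.3.1 retests off drug until platelets are normal, so such a patient's recovery can be recorded during the hold. If treatment resumes, the duration is positive and nothing in the output shows that recovery occurred off drug. Amendment 2 reports three temporary interruptions among the 11 reduced patients (3/11 = 27%), at the earlier starting dose.

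**The case against.** **The condition is narrow. This stands.** Recovery is the first normal value after the nadir. A patient who is low at Visit 11 but had one normal on-drug count after the nadir has already recovered. He belongs under additional decrease after recovery, with a positive duration. The Visit 12 problem needs every count from nadir to last dose to be below normal.

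**Other outputs show persistent low counts. This stands.** SAP 6.4.4 also gives platelet summaries at each time point by arm, with Visit 11 separate from Visit 12. It adds shift tables on the worst on-treatment value, listings of out-of-range values and box-plots over time. A reader might infer that the written rule hides non-recovery from the study report. It does not; it distorts these particular variables.

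**The group is not necessarily emptied. This stands.** A reader might infer that nobody would remain under time on treatment without recovery. Visit 12 is for completers, and an early withdrawal may be seen before washout or have no later count.

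**No proportion can be given. This stands.** It is tempting to take the 11 reduced patients in Amendment 2 as a denominator. Reduction is triggered by two consecutive counts at or below 150 x 10^9/L, whereas recovery applies only to minima below LLN, which the documents do not state. Those 11 also started on the earlier dose.

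**The nadir should not be limited to on-drug counts. This stands.** Section 7.3.1 requires a count at or below 50 x 10^9/L to be repeated with treatment stopped, and schedules retests during interruptions. The true drug-caused minimum may be among those counts.

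**Data cut-off avoids the negative value. This does not rescue the rule.** By Step 2 it labels off-drug days as time on treatment. A negative duration might be noticed in the output, but the patient's absence from the non-recovery variable would be harder to see.

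**Conclusion.** The point holds as an omission with a definite consequence. SAP 6.4.4 admits off-drug counts as recovery, and nothing else in the SAP excludes them. A dose-reduced patient with no normal count from nadir to last dose who normalises at Visit 12 is misclassified as recovered. His duration is -28 days (-21 to -35) under one end date and consists of off-drug days under the other. He is also lost from time on treatment without recovery (84 days in the worked example).

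The size per patient follows from the schedule; the number of patients does not. It depends on the LLN, on how many reduced patients fall below it, and on how many stay low to the last dose. That their Visit 12 counts would be normal assumes that the washout reported in earlier studies applies here.

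The affected outputs are descriptive safety summaries in one subgroup, so the primary analysis is untouched. The definition should still be corrected, because it can report non-recovery on drug as recovery.

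**What to change.** In SAP 6.4.4:

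1. Keep the nadir as the minimum over all post-baseline counts, including those taken during a hold.
2. For *time on treatment after recovery*, *additional platelet decrease after recovery* and *time on treatment without recovery*, define recovery as the first normal count after the nadir taken on study drug, that is, up to the last dose and outside interruptions.
3. Report normalisation during an interruption, and normalisation after the last dose (Early Withdrawal Visit or Visit 12), on separate lines.
4. End *time on treatment after recovery* at the earlier of the last treatment date and the data cut-off.
5. Because the nadir stays unrestricted, list separately any patient whose minimum falls after the last dose; otherwise *time on treatment without recovery* would be negative for him.

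The cost is SAP wording and a date filter using dosing and interruption dates. No new data, visits or changes to patient management are needed. The on-treatment recovery figures may look less favourable, and splitting a small subgroup across more lines leaves few patients in each.
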